4.6.1.2 Presentation

Total (or intended) exposure, actual exposure, number of cycles received, RDI, and number of dose interruptions, dose reductions, and dose modifications (either a dose interruption or

a dose reduction) will be summarised for each treatment group and treatment. Exposure will be summarised for the randomised period and on-selumetinib safety analysis set. For the randomised period safety analysis set, the exposure will be separated by placebo and selumetinib. For the on-selumetinib safety analysis set, the exposure will be separated by treatment arm and will include an overall summary.

Exposure data will be listed. Date of first exposure to treatment, total exposure (days), actual exposure (days), number of cycles received, RDI and compliance to IP will be summarised at period-level for the randomised period and on-selumetinib period. Additionally, details on all dose interruptions and reductions will be summarised including, reason for action taken, start and end date of interruption/reduction and dose per administration.

Percentage treatment compliance summarised as a continuous variable and counts using categories: eg, 100%, $\geq 95\% - < 100\%$, $\geq 90\% - < 95\%$, and $\geq 80\% - < 90\%$, etc.

4.6.2 Adverse Events

4.6.2.1 Definitions and Derivations

The MedDRA (using the latest MedDRA version) is used to code AEs. AEs are graded according to the CTCAE version 5.0.

Treatment-emergent AEs will be assigned to treatment-emergent periods, as described in Section 3.3.2.4. The same treatment-emergent AE can be assigned to both treatment periods (e.g., AE starts during the randomised period but worsens during the on-selumetinib period).

AEs of Special Interest

Some clinical concepts (including some selected individual PTs and higher-level terms) have been considered “AEs of special interest” (AESIs) to the selumetinib program.

The AESIs in CSP Table 9 have been identified as a list of categories by the patient safety team.

Other Significant Adverse Events (OAEs)

During the evaluation of the AE data, an AstraZeneca medically qualified expert will review the list of AEs that were not reported as serious AEs (SAEs) and AEs leading to discontinuation. Based on the expert’s judgement, significant AEs of particular clinical importance may, after consultation with the Global Patient Safety Physician, be considered OAEs and reported as such in the CSR.

A similar review of laboratory/vital signs/ECG data will be performed for identification of OAEs. Examples of these could be marked haematological and other laboratory

abnormalities, and certain events that lead to intervention (other than those already classified as serious), dose reduction, or significant additional treatment.

4.6.2.2 Presentation

Summary tables of the number and percentage of patients with AEs by SOC and PT will be produced for below categories. An overall summary table will include the number and percentage of patients in each category.

- All AEs
- AEs possibly related to study intervention
- AEs of CTCAE grade 3 or higher
- AEs with CTCAE grade 3 or higher, possibly related to study intervention
- AEs with an outcome of death
- AEs with an outcome of death possibly related to study intervention
- All SAEs
- SAEs possibly related to study intervention
- AEs leading to discontinuation of study intervention
- AEs leading to discontinuation of study intervention, possibly related to study intervention
- AEs leading to dose interruption of study intervention
- AEs leading to dose reduction of study intervention
- AESIs
- OAEs

Patients with more than one event in any category are only counted once in each category (i.e., multiple events are not accounted for).

Additionally, the most common AEs, which are those AEs that occur in at least 10% of patients overall, are summarised by PT and by decreasing frequency. This cut-off may be modified after review of the data. When applying a cut-off (eg, 10%), the raw percentage should be compared to the cut-off, and no rounding should be applied first (ie, an AE with frequency 9.9% does not appear if the cut-off is 10%).

A separate table will present non-serious AEs occurring in more than 5% of patients in any treatment group.

CTCAE grades and summaries of the number and percentage of patients will be provided by SOC, PT, and maximum reported CTCAE grade. A summary table of AESIs by maximum reported CTCAE grade will be produced.

Each summary table above will be presented for TEAEs during the randomised period and for TEAEs during the on-selumetinib period as defined in Section 3.3.2.4.

For the summaries of on-selumetinib TEAEs, in addition to number and number and percentage of patients [n(%)], exposure-adjusted incidence rates (per 100 person-years) will be reported. These are derived as:

$$\frac{\text{Number of participants with AE}}{\text{Total on - selumetinib person - years}} \times 100$$

where the total on-selumetinib person-years is given by the sum of all the individual durations of exposure until experiencing the first occurrence of the AE across all patients in the on-selumetinib period. For those patients experiencing the AE, duration of exposure will be calculated as (first occurrence AE start date – first selumetinib dose date +1)/365.25. For those patients not experiencing the AE, it will be equal to (min(last selumetinib dose date +30 days, date of study discontinuation, DCO) – first selumetinib dose date +1)/365.25.

The number of patients in the placebo treatment group might differ for the randomised period and on-selumetinib period. Patients who were randomised and treated with placebo but discontinued prior to them being able to start on selumetinib will not be counted in the on-selumetinib period but will be counted in the randomised period.

All reported AEs will be listed for the safety analysis set. The key listings which will be produced are the following:

- AEs with an outcome of death – key subject information
- SAEs – key subject information
- AEs leading to discontinuation of study intervention – key subject information
- AEs leading to dose modification (dose interruption and/or dose reduction of study intervention) – key subject information
- AESIs – key subject information
- All AEs – listing of key information

Key listings will be split by treatment group using subheadings.

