#### **9.4.3.1 Adverse Events**

Adverse events will be coded using the most recent version of MedDRA that will have been released for execution at AstraZeneca/designee.

Adverse events will be presented for each treatment group by SOC and/or PT covering number and percentage of participants reporting at least one event and number of events where appropriate.

An overview of AEs will present for each treatment group the number and percentage of participants with any AE, AESIs, AEs with outcome of death, serious AEs, and AEs leading to discontinuation of study treatment, as well as AEs leading to study treatment dose interruptions and AEs leading to study treatment dose reductions.

Separate AE tables will be provided that take different factors into consideration, including relationship as assessed by the investigator, maximum CTCAE grade, seriousness, death and events leading to discontinuation of study intervention as well as other action taken related to study treatment, events of special interest and other significant AEs.

An additional table will present number and percentage of participants with most common AEs. Most common (eg, frequency of  $> x\%$ ,  $\geq x\%$ ) will be defined in the SAP.

In accordance with the requirements of the FDA, a separate table will present non-serious AEs occurring in more than 5% of participants in any treatment group.

Key participant information will be presented for participants with AEs with outcome of death, serious AEs, and AEs leading to discontinuation of study intervention.

An AE listing for the safety analysis set will cover details for each individual AE.

Full details of AE analyses will be provided in the SAP.

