It is estimated that approximately 212 adult patients will be enrolled at approximately 46 sites across 13 countries to achieve approximately 146 patients randomised to study intervention. Patients will be randomised 1:1 to receive selumetinib or placebo (i.e. 73 patients per arm). Randomisation will be stratified at the central level by average baseline PAin INTensity Scale for Plexiform Neurofibroma (PAINS-pNF) chronic target PN pain score (< 3 and \geq 3) and geographical region (Europe, China, Japan, and Rest of World). A blocked randomisation will be generated, and randomisation will be balanced within the IRT at the central level. The number of patients randomised will be capped at approximately 106 patients with an average baseline PAINS-pNF chronic target PN pain score \geq 3 and approximately 40 patients with an average baseline PAINS-pNF chronic target PN pain score < 3. Patients randomised to selumetinib will receive selumetinib 25 mg/m² orally twice daily (bid) (based on body surface area [BSA], capped at 50 mg bid when BSA is \geq 1.9 m²) in 28-day cycles until a selumetinib discontinuation criterion is met. Patients randomised to placebo will receive placebo orally bid and will receive selumetinib treatment after the end of Cycle 12. Selumetinib capsules will be administered using BSA-based dosing. If it is anticipated that 20% or more of patients (across blinded study intervention groups) withdraw prior to the end of Cycle 16 for reasons other than progression, then recruitment rates notwithstanding, enrolment will continue to randomise at least 50% of the total number of dropout patients to ensure that the primary endpoint is adequately powered.

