3.3.2.4 Treatment-emergent Periods

The analysis of treatment-emergent adverse events (TEAEs) and concomitant medication will be performed separately for TEAEs occurring/concomitant medication taken during the safety randomised period and TEAEs occurring/concomitant medication taken during the on-selumetinib period. While the analysis of TEAEs in the safety randomised period will be comparative of the two treatment groups, TEAEs presented for the on-selumetinib period will be not comparative due to the different exposure periods. To note, the two safety analysis periods are not mutually exclusive.

TEAEs and Concomitant Medication during the Safety Randomised Period

For patients receiving any selumetinib in the safety randomised period, an adverse event (AE) or a concomitant medication is considered treatment emergent during the safety randomised period if the start date/time of the event or worsening date/time (only for AEs) occurs between the date of first dose of study intervention (Cycle 1 Day 1) and last dose of Cycle 12 or date of study intervention discontinuation (end of treatment [EOT]) + 30 days or DCO date, whichever comes first.

For patients receiving placebo in the safety randomised period, an AE or a concomitant medication is considered treatment emergent during the safety randomised period if the start date/time of the event, or worsening date/time of an AE occurs between the date of first dose of placebo (Cycle 1 Day 1) and the crossover date or date of early placebo discontinuation + 30 days or DCO, whichever comes first.

A worsening is defined as having any on-treatment severity during the safety randomised period worse than the baseline severity. The reported severity of an AE that is treatment emergent during the safety randomised period is given by the maximum Common

Terminology Criteria for Adverse Events (CTCAE) grade recorded any time on-treatment during the safety randomised period. The reported outcome of an AE will be the last outcome corresponding to the maximum CTCAE grade recorded on-treatment in the safety randomised period. Seriousness and causality during the randomised period will also be reported as the worst value recorded in the safety randomised period.

TEAEs and Concomitant Medication during the On-Selumetinib Period

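### The 10% cut-off for the most-common-AE table pools both arms, so in the randomised period an event seen only on selumetinib needs about 20% to be listed (minor)

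*SAP*

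**What the plan says.** Protocol 9.4.3.1 asks for the table and leaves its definition to the SAP: "An additional table will present number and percentage of participants with most common AEs".

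SAP 4.6.2.2 supplies the definition: "the most common AEs, which are those AEs that occur in at least 10% of patients overall, are summarised by PT". On applying it, "the raw percentage should be compared to the cut-off, and no rounding should be applied first". It adds: "This cut-off may be modified after review of the data".

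The next paragraph of the same section uses a different denominator for another table, which covers "non-serious AEs occurring in more than 5% of patients in any treatment group".

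Both tables fall under the instruction that "Each summary table above will be presented for TEAEs during the randomised period" and again for the on-selumetinib period. SAP 3.3.2.4 separates the two periods: "While the analysis of TEAEs in the safety randomised period will be comparative of the two treatment groups", whereas the on-selumetinib presentation is not comparative because exposure differs.

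SAP 3.3 limits overall totals to baseline summaries. For China, SAP 8.3 and Table 19 give only a frequency of 10% or more, with no denominator.

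**The concern.** A table of common events for a two-arm comparison should show what is common on either treatment. A pooled cut-off does this only when the arms have similar rates. When an event is concentrated in one of two equal arms, pooling halves its rate. Events that occur on selumetinib with little or no placebo background then face a higher bar than events occurring equally in both arms.

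The section already contains the per-arm form, one paragraph later, for the 5% table. The pooled form therefore looks like an oversight in wording rather than a considered choice. At stake is the choice of rows in one descriptive table for the only controlled safety period.

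**Working it through.** **Inputs**
- Cut-off: 10%, pooled, unrounded (SAP 4.6.2.2).
- Arms: 1:1, 73 each, 146 in total (SAP 1.1).

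The plan gives no count or per-arm rate for this cut-off, so there is no figure of its own to reproduce. The arm size does reproduce from SAP 3.4: 42 per arm with 20% drop-out gives 42 / 0.8 = 52.5, rounded up to 53; 2 × 53 = 106; 106 + 40 = 146, or 73 per arm.

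**Entry condition under the pooled rule**

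Let *a* and *b* be the participants with the event on selumetinib and placebo. The term is listed if (a + b) / 146 ≥ 0.10. Since 0.10 × 146 = 14.6, this means a + b ≥ 15.

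| Selumetinib | Placebo | Pooled | Listed? |
|---|---|---|---|
| 14/73 (19.2%) | 0/73 | 14/146 = 9.6% | No |
| 15/73 (20.5%) | 0/73 | 15/146 = 10.3% | Yes |
| 12/73 (16.4%) | 2/73 (2.7%) | 14/146 = 9.6% | No |
| 8/73 (11.0%) | 7/73 (9.6%) | 15/146 = 10.3% | Yes |

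The condition can be rewritten as b ≥ 15 − a. For a given selumetinib count below 15, the fewer the placebo events, the more likely the term is to be dropped.

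**Entry condition under an either-arm rule**

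0.10 × 73 = 7.3, so 8 participants in one arm suffice (8/73 = 11.0%; 7/73 = 9.6% fails). Selumetinib-only events in 8 to 14 participants (11.0% to 19.2%) would be listed; the pooled rule omits them.

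**Chance of omission**

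For an event that never occurs on placebo and has true rate π on selumetinib, the pooled rule omits it with probability P(X ≤ 14), where X is binomial (73, π):

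| π | Probability omitted |
|---|---|
| 10% | 99.5% |
| 12% | 97.5% |
| 15% | 87.6% |
| 18% | 67.0% |
| 20% | 50.0% |

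**Sensitivity to the number treated**

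The documents do not give safety-set sizes. The largest omitted selumetinib-only count is:
- 145 treated: 14, which is 14/73 = 19.2% or 14/72 = 19.4%, depending on which arm has 72.
- 70 per arm: 13, which is 13/70 = 18.6%.
- 50 per arm: 9, which is 9/50 = 18.0%.

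The effect comes from pooling two equal arms, not from the exact total.

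**The case against.** The strongest reply is that the omitted events are reported elsewhere in the same section. SAP 4.6.2.2 plans a table of all AEs by system organ class and preferred term with no cut-off, for the randomised period and by arm. The 14 versus 0 and 12 versus 2 examples both appear there. Non-serious occurrences also enter the 5% table once 4 participants in one arm have them (0.05 × 73 = 3.65; 4/73 = 5.5%), and serious ones enter the SAE table. No count or arm comparison is lost. This stands, and it limits the weight of the point.

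A second reply is that *overall* is undefined and sits awkwardly with SAP 3.3, which confines overall totals to baseline summaries. That is fair, but pooling remains the natural reading, because the next paragraph names treatment groups when a per-arm rule is meant. If pooling was not intended, the same edit removes the ambiguity.

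Third, the rule selects on frequency, not on relation to treatment. Selumetinib-only events at 20.5% or more are listed, and events with some placebo background enter at lower selumetinib rates. A reader might infer that the table filters out treatment-related events in general. The documents do not support that: the affected band is limited, and Protocol Table 3 describes rash and gastrointestinal effects as frequent, so these are the events least likely to be missed.

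Fourth, safety data are descriptive (Protocol 9.4.3). Significance tests on chosen examples would add weight that the plan does not give them, so none are used here.

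**Conclusion.** The point holds as a minor one. Under the pooled reading, the randomised-period table of most common AEs requires about 20% for an event seen only on selumetinib (15/73 enters, 14/73 does not) and about 10% per arm for a balanced event. It therefore under-selects selumetinib-specific events between roughly 11% and 19%. This rests on reading *overall* as both arms combined and on about 73 treated per arm; with 50 to 73 per arm the upper end of the band stays between 18% and 19.4%.

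Three stronger inferences are not supported:
- That the report as a whole makes selumetinib look better tolerated. The uncut table of all AEs shows every such event by arm.
- That this table carries special weight in the study report text or in labelling. The documents say nothing of the kind; the protocol calls it only an additional table.
- That permission to change the cut-off after data review is itself a source of bias. It concerns a display threshold in an untested table, the threshold can move either way, and the uncut table is unaffected. Whether to keep that sentence is a matter of preference.

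**What to change.** In SAP 4.6.2.2, for the randomised-period table, select preferred terms with a raw frequency of 10% or more in either treatment group, matching the form already used for the 5% non-serious table. Keep the pooled rule only for the on-selumetinib table, which is not comparative and in which everyone receives selumetinib. State the either-group denominator for the China randomised-period table as well, since SAP 8.3 and Table 19 currently name none.

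The cost is one phrase in 4.6.2.2, a clarification in the China appendix and a few more table rows. No new data or analyses are needed.

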4.6.3 Clinical Laboratory, Blood Sample

4.6.3.1 Definitions and Derivations

Blood samples for the determination of clinical chemistry and haematology will be taken at the visits indicated in the CSP.

The rules described in Sections [3.3.1](#), [3.3.3](#), [3.3.4](#), and [3.3.5](#) of this document considering definition of baseline, visit windows, and handling multiple records and records above or below the limit of quantification are followed.

Absolute values are compared to the reference range and classified as low (below range), normal (within range or limits of range), and high (above range). Local reference ranges are used for the primary interpretation of laboratory data.

Changes from baseline in clinical chemistry and haematology will be calculated for each post-dose visit on treatment, where on treatment includes all data collected between the first dose of selumetinib until the earlier of last dose of study intervention + 30 days, or DCO.

All laboratory results will be converted to standard units, and CTCAE grades (version 5.0) will be derived at each visit according to the CTCAE grade criteria. Parameters for which CTCAE grades are defined may have both high and low range values, CTCAE grades will be calculated for each set of high and low values in those cases. Laboratory parameters that will be summarised, along with details of whether maximum and/or minimum are of interest and availability of CTCAE grading, are given in [Table 17](#).

Table 17: Haematology and Clinical Chemistry Parameters – Minimum/Maximum of Interest

Laboratory assessment	Maximum of interest	Minimum of interest	CTCAE grading available
ALT	Yes		Yes
AST	Yes		Yes
Alkaline phosphatase	Yes		Yes
Total bilirubin	Yes		Yes
Magnesium	Yes	Yes	Yes
Sodium	Yes	Yes	Yes
Potassium	Yes	Yes	Yes
Creatinine	Yes		Yes
Total calcium	Yes	Yes	No
Blood urea nitrogen	Yes		No
Creatine kinase	Yes		Yes
Haemoglobin	Yes	Yes	Yes
Lymphocytes (absolute)	Yes	Yes	Yes

Table 17: Haematology and Clinical Chemistry Parameters – Minimum/Maximum of Interest

Laboratory assessment	Maximum of interest	Minimum of interest	CTCAE grading available
Neutrophils (absolute)		Yes	Yes
Leukocytes (absolute)		Yes	Yes
Total red blood cell count		Yes	No
Platelets		Yes	Yes
Albumin		Yes	Yes
Total Protein		Yes	No
Amylase	Yes		Yes
Gamma-glutamyl transferase	Yes		Yes
Phosphate	Yes	Yes	No

ALT, alanine aminotransferase; AST, aspartate aminotransferase; CTCAE, Common Terminology Criteria for Adverse Events.

For parameters with no CTCAE grading that are listed in [Table 17](#), any increase/decrease and treatment-emergent laboratory change (TELC) is derived. An on-treatment increase is defined as an increase to a value above the upper local laboratory reference limit at any time on treatment for patients with a value below the upper local laboratory reference limit at baseline. An on-treatment decrease is defined as a decrease to any value below the local laboratory reference range limit at any time on treatment for patients with a value above the lower local laboratory reference limit at baseline. A TELC is defined as any on treatment increase or decrease from baseline.

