3.2.11 Summary of Outcome Variables and Analysis Sets

The analysis sets for each outcome variable are provided in [Table 1](#). For some outcome variables, the analysis set will use a further subset (e.g., patients who are evaluable for the analysis of duration of response (DOR) are those who responded in the ORR analysis) which are described in detail in the endpoint analysis sections in [Section 4.2](#).

Table 1 Summary of Outcome Variables and Analysis Sets

Outcome variable	Analysis set
Efficacy data	
ORR by the end of Cycle 16 (primary endpoint)	FAS
Change from baseline in PAINS-pNF chronic target PN pain intensity score at Cycle 12 (1 st key secondary endpoint)	Pain FAS
Change from baseline in PlexiQoL total score at Cycle 12 (2 nd key secondary endpoint)	FAS and Pain FAS (supplementary)
Chronic target PN pain palliation, time to chronic target PN pain palliation	Pain FAS
ORR (single arm), DOR (single arm), PFS (single arm), time to progression (single arm), time to response (single arm), and BOR (single arm)	Selumetinib FAS, Extended Selumetinib FAS, and FAS (selumetinib arm only)
PFS during the randomised period (exploratory endpoint)	FAS
Best percentage change from baseline in target PN volume during the randomised period	FAS
Pain medication, PII-pNF pain interference total score, PROMIS Physical Function items, Peds QL Inventory (NF1 Module Acute Version 3.0 – Adult Report), Skin Sensations Domain, EQ-5D-5L, EQ-VAS, PAINS-pNF spike target PN pain intensity score	FAS

Table 1 Summary of Outcome Variables and Analysis Sets

Outcome variable	Analysis set
Percentage change from baseline in target PN volume at Cycle 30 or later.	Fed FAS
Study Population/Demography Data	
Demography characteristics (e.g., age, sex, etc.)	FAS
Baseline and disease characteristics	FAS
Important deviations	FAS
Medical/surgical history	FAS
Previous anti-PN therapy	FAS
Concomitant medications/procedures	FAS
Subsequent anti-PN therapy	FAS
PK Data	
Selumetinib and N-desmethyl selumetinib plasma concentration data and PK parameters	PK
Safety data	
Exposure	Randomised period SAF and On-selumetinib SAF
Adverse events	Randomised period SAF and On-selumetinib SAF
Laboratory measurements	Randomised period SAF and On-selumetinib SAF
Vital signs	Randomised period SAF and On-selumetinib SAF
ECGs	Randomised period SAF and On-selumetinib SAF
Ophthalmologic assessment	Randomised period SAF and On-selumetinib SAF
Physical Examinations	Randomised period SAF and On-selumetinib SAF

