3.3.2.3 On-Treatment Safety Period

For the purposes of summarising safety data assessed at visits, in addition to baseline data, only on-treatment data are included in the summary tables. On-treatment data will be defined as data from the first dose of study intervention until the last dose of study intervention + 30 days.

The On-Treatment Safety Period will be further subset into the On-treatment Safety Randomised Period and On-selumetinib Safety Period.

If the On-Treatment Safety Period of a patient is still ongoing at the time of the analysis, their on-treatment safety period will be truncated at the DCO date, and any measurement/event with a start date after the DCO date will be presented at a later DCO.

On-treatment Safety Randomised Period.

The on-treatment safety randomised period for patients receiving selumetinib in the randomised period will be defined as the date from the first dose of study intervention until the first date when the selumetinib kit(s) are dispensed as recorded in the drug accountability form at or after the Cycle 12 Day 28 visit date or 30 days after study intervention discontinuation or up to one day prior to start of subsequent therapy, whichever occurs first.

The on-treatment safety randomised period for patients receiving only placebo in the randomised period will be defined as the date from the first dose of study intervention until the date when the first selumetinib kit(s) are dispensed as recorded in the drug accountability form (crossover date) or 30 days after placebo discontinuation or up to one day prior to the start of subsequent therapy, whichever occurs first.

If the on-treatment randomised period of a patient is still ongoing at the time of the analysis, their on-treatment randomised period will be truncated at the DCO date, and any measurement/event with a start date after the DCO date will be presented at a later DCO.

On-Selumetinib Safety Period

The on-selumetinib safety period will be defined as the date from the first dose of selumetinib until 30 days after the last dose of selumetinib or up to one day prior to the start of subsequent therapy, whichever occurs first.

The baseline definition for patients receiving placebo in the randomised period and then crossing over to selumetinib either on Cycle 13 Day 1 or earlier in the case of progression will differ for the on-treatment safety randomised period and the on-selumetinib period as described in Section [3.3.1](#).

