If the on-selumetinib period of a patient is still ongoing at the time of the analysis, their on-selumetinib period will be truncated at DCO date, and any measurement/event with a start date after the DCO date will be presented at a later DCO.

Table Presentation

Tables for the on-treatment during the randomised period will be presented by patients who received only placebo and patients who received any selumetinib.

Tables for the On-selumetinib Safety Period will be presented by patients who received selumetinib from the start of the randomised period and patients who received selumetinib after crossing over from placebo.

The baseline definition for patients receiving placebo and then starting on selumetinib treatment (post crossover) will differ for the on-treatment during the randomised period and the on-selumetinib period as described in Section 3.3.1.

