4.6.3.2 Presentations

Only on treatment laboratory data as defined in Section [3.3.2.3](#) are included in the summary tables. The same section describes the treatment period definitions and provides further information on the presentation of the tables. Haematology and clinical chemistry data will be summarised by treatment group and scheduled visit using descriptive statistics over time in terms of absolute values and changes from baseline for each treatment period.

Shift tables showing CTCAE grades from baseline to worst CTCAE grade on treatment will be produced for each treatment period for parameters with available CTCAE grades (see [Table 17](#)). Hyper- and/or hypo-directionality will be indicated in the parameter's labels. Percentages are based on the number of patients with a baseline value and an on-treatment value.

For parameters in [Table 17](#) with no CTCAE grading (“No” for CTCAE grading available), the number and percentage of patients with any on treatment increase from baseline, any on treatment decrease from baseline, and a TELC is summarised. Percentages are based on the

number of patients with a baseline value below/above the local laboratory upper/lower reference limit and an on-treatment value for the any increase/decrease summaries, respectively. Percentages for a TELC are based on the number of patients with a baseline value and an on-treatment value.

Haematology and clinical chemistry data in [Table 17](#) will also be presented graphically for each treatment period using boxplots for absolute values and changes from baseline by scheduled visit.

A table will be provided for patients with potential Hy's law (alanine aminotransferase [ALT] or aspartate aminotransferase [AST] $\geq 3 \times$ upper limit of normal [ULN], and total bilirubin $\geq 2 \times$ ULN), where the onset date of ALT or AST elevation is prior to or on the date of total bilirubin elevation.

Laboratory data for the variables listed in the CSP Table 8 will be listed. Site reference ranges will also be listed. Flags (H or L) will be applied to values falling outside the reference ranges (which will be explicitly noted on these listings where applicable), and for the CTCAE grade for parameters for which CTCAE grading applies.

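### SAP 4.6.3.1 opens the laboratory change-from-baseline window at the first selumetinib dose, in conflict with Sections 3.3.2.3 and 4.6.3.2, which keep placebo-period changes

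*SAP*

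**What the plan says.** SAP Section 4.6.3.1 limits laboratory changes from baseline to post-dose visits on treatment, and supplies its own meaning for the term: "on treatment includes all data collected between the first dose of selumetinib until the earlier of last dose of study intervention"; the window closes 30 days after that dose or at the data cut-off, whichever comes first.

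Section 3.3.2.3 sets the general rule for safety data collected at visits: "On-treatment data will be defined as data from the first dose of study intervention until the last dose of study intervention + 30 days". It then splits this into two periods. For the first, the placebo rule begins: "The on-treatment safety randomised period for patients receiving only placebo in the randomised period will be defined as the date from the first dose of"; the dose meant is that of study intervention. It closes the placebo window at dispensing of the first selumetinib kits, 30 days after placebo discontinuation, or the day before subsequent therapy, whichever is first. The second, the on-selumetinib safety period, starts at the first selumetinib dose. Tables for the randomised period "will be presented by patients who received only placebo and patients who received any selumetinib".

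Section 4.6.3.2 states which window the laboratory tables use: "Only on treatment laboratory data as defined in Section [3.3.2.3](#) are included in the summary tables". It asks for haematology and chemistry by treatment group and visit, "in terms of absolute values and changes from baseline for each treatment period". SAP Table 1 assigns laboratory measurements to the "Randomised period SAF and On-selumetinib SAF". Protocol Section 9.4.3.4 likewise plans observed values and changes from baseline for each treatment group, and SAP Section 2 lists no departure from that.

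**The concern.** The derivation subsection and the presentation subsection for the same data give different windows. One starts at selumetinib, the other at study intervention. For participants randomised to selumetinib the two starts fall on the same day. For placebo participants they are about 12 cycles apart, so the discrepancy affects one arm only.

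The presentation subsection decides which records enter a table, while the derivation subsection decides for which visits a change is calculated at all. A table filter built on Section 3.3.2.3 cannot restore changes that were never derived. The first 12 cycles are the only placebo-controlled stretch of the trial. ALT, AST and creatine phosphokinase increases are among the adverse events of special interest in Protocol Table 9, so placebo changes over those cycles are useful context.

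The term could also travel. The same subsection uses *on treatment* to define on-treatment increase, on-treatment decrease and treatment-emergent laboratory change (TELC).

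**Working it through.** The documents give no figure to reproduce. The check sets the windows side by side and then counts the visits affected.

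**1. Windows compared**

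| | 4.6.3.1 | 3.3.2.3, randomised period, placebo-only | 3.3.2.3, on-selumetinib period |
|---|---|---|---|
| Start | First selumetinib dose | First dose of study intervention | First selumetinib dose |
| End | Last study intervention + 30 days, or data cut-off | Crossover kit dispensing, placebo discontinuation + 30 days, or day before subsequent therapy | Last selumetinib dose + 30 days, or day before subsequent therapy |
| Baseline (3.3.1) | By reference to 3.3.1 | Last value before first study intervention | Last value before first selumetinib |

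The start in 4.6.3.1 fits the on-selumetinib period but not the randomised period. Its end fits neither exactly: it has no crossover limit and no subsequent-therapy limit. It opens on *selumetinib* and closes on *study intervention*, which looks like a drafting slip.

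**2. Scheduled placebo visits affected by the literal sentence**

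- Post-baseline laboratory visits before crossover (Protocol Table 1): Day 28 of Cycles 1, 2, 4, 6, 8, 10 and 12 = 7.
- Planned placebo arm (Protocol Section 9.2): 73.
- First selumetinib dose on placebo (Protocol Sections 1.1 and 6.1.1): after the end of Cycle 12, earlier only with progression on imaging determined by central review.

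Visits with no derived change = participants x visits = 73 x 7 = 511. This is an upper limit, before dropout and early crossover. It takes the Cycle 12 sample as drawn before the first selumetinib dose, in line with the note to Table 1 that dispensing follows the assessments.

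| Rule applied | Placebo visits lost | Selumetinib-arm visits lost |
|---|---|---|
| 4.6.3.1 as written | up to 511 | 0 |
| 3.3.2.3 | 0 | 0 |

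A placebo participant who never crosses over would have no on-treatment change at all under 4.6.3.1.

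**3. Where the term is reused**

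The increase, decrease and TELC definitions apply to the parameters that SAP Table 17 marks as having no CTCAE grading: total calcium, blood urea nitrogen, red cell count, total protein and phosphate, that is 5 parameters. Percentages for TELC and for the CTCAE shift tables in 4.6.3.2 also require an on-treatment value, so a literal reading could alter placebo denominators there.

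**4. Comparison with other safety sections**

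Vital signs, echocardiogram, ophthalmology and ECOG (SAP 4.6.6.2, 4.6.8.2, 4.6.9.2, 4.6.11.2) refer to Section 3.3.2.3 and give no competing definition. Section 4.6.3.1 cites 3.3.1, 3.3.3, 3.3.4 and 3.3.5 but not 3.3.2. The laboratory section is the exception.

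**The case against.** The strongest reply is that the plan already settles the matter. Section 4.6.3.2, the next subsection, makes Section 3.3.2.3 govern every laboratory summary table and asks for changes from baseline by group and period. Section 3.3.2.3 gives placebo-only patients their own window and column, the Randomised Period SAF retains a placebo group, and the baseline for that set precedes the first dose of study intervention. A careful programmer would follow these. That stands as evidence of intent, and it is why the point is minor. It does not make the derivation sentence correct, because a derived dataset built from 4.6.3.1 would lack the values that 4.6.3.2 tabulates.

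A reader might infer three stronger things, none of which the documents support:

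- *The control arm is removed from laboratory safety.* The sections just listed specify it repeatedly; one sentence read alone does not undo them.
- *The only controlled comparison for creatine kinase and transaminases is lost.* The sentence concerns changes from baseline. Absolute values by visit are unaffected. CTCAE grades are derived at each visit and shown in shift tables by period, there is a potential Hy's law table based on multiples of the upper limit of normal, and adverse events of special interest are tabulated for the randomised period.
- *Post-crossover values would fill the placebo column of the randomised-period tables.* Section 3.3.2.3 ends that window at crossover, so they cannot.

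**Conclusion.** Wrong as written: an internal inconsistency between SAP 4.6.3.1 and SAP 3.3.2.3 with 4.6.3.2. If 4.6.3.1 is programmed literally, up to 511 scheduled placebo visits carry no laboratory change from baseline, and the wording may carry into the TELC definitions. If 3.3.2.3 is followed, as 4.6.3.2 directs for the tables, nothing is lost. The count assumes the planned 73 placebo participants, full attendance and no early crossover.

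Severity is minor. The matter is confined to descriptive safety summaries, the intended analysis is clear from the surrounding sections, and no alpha level, power figure or efficacy test depends on it.

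**What to change.** In SAP 4.6.3.1, delete the local definition of *on treatment* and state that changes from baseline are calculated separately for the on-treatment safety randomised period and the on-selumetinib safety period of Section 3.3.2.3, each with its own baseline from Section 3.3.1. State that the same periods apply to the on-treatment increase, decrease and TELC definitions.

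Replacing only *selumetinib* by *study intervention* at the start of the window would restore the placebo visits, but would leave an end that still differs from Section 3.3.2.3 on crossover and subsequent therapy. The cross-reference settles both ends.

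The cost is one or two sentences in the SAP and a check that the laboratory derivation program uses the 3.3.2.3 windows. No new data, analysis or protocol change is needed.
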